 10. 11. 12. 13. 14. 15. 16. 17. 18. 	Products, Devices, Techniques, and Tools.22Safety Reporting22Statistics and Analysis26Data Management28Quality Assurance Procedures30Ethical and Regulatory Considerations32Finance and Insurance33Publication and Registration Policy34References35

Bwrdd Iechyd Prifysgol Caerdydd a'r Fro Cardiff and Vale University Health Board

٦

1. Study Synopsis

Study Title	A pilot study investigating the effects of a manuka honey sinus rinse on sino-nasal outcome test scores in cystic fibrosis patients.				
Short Title	Manı	Manuka honey sinus rinse study – V0.1			
Study Design	Basic	Basic Science (feasibility / pilot study)			
Planned Sample Size	20-40) Participan	ts		
Planned Study Period	18 M	onths			
Planed Study Period		Start:	01/10/2018	Finish:	31/03/2020
Primary Objective	Does the addition of manuka honey to the sinus rinse impact on the Sino Nasal Outcome Test (SNOT)-22 score of patients with cystic fibrosis?				
Secondary Objective(s)	1. Does the addition of manuka honey to a sinus rinse alter the quality of life of patients with cystic fibrosis?				
	2.	Does the addition of manuka honey to a sinus rinse impacton the bacterial type/amount found in the nasal/paranasal cavities of patients with cystic fibrosis?			
	Does the addition of manuka honey to a sinus rinse protocolchange the structure of sputum mucus in patients with cystic fibrosis?				
Statistical Methodology & Analysis	Sino-nasal outcome tests and quality of life (questionnaire) scores will be compared before and after treatment with/without the manuka honey sinus rinse. Proportional change in bacteria seen within and between groups will be analysed using a contingency table and assessing co-variants. The molecular structural changes to sputum mucus will be corrected and vector normalized.				

Bwrdd Iechyd Prifysgol Caerdydd a'r Fro Cardiff and Vale University Health Board

2. Abbreviations

AE	A dverse E vents
AMR	A nti m icrobial R esistance
APR	Annual Progress R eport
AWACFC	A ll W ales A dult Cystic F ibrosis C entre
BMI	Body Mass Index
CF	C ystic F ibrosis
CFQ-R	C ystic F ibrosis Q uestionnaire - R evised
CI	C hief I nvestigator
CRF	C ase R eport F orm
СТ	C omputed T omography
ECFSPR	E uropean Cystic F ibrosis S ociety P atient R egistry
FEV1%	E orced E xpiratory V olume (in 1 second as percentage of predicted)
GCP	G ood C linical P ractice
GP	G eneral P ractitioner
ICH	International Conference of Harmonisation
ISF	Investigator Site File
HCRW	H ealth and C are R esearch W ales
HRA	H ealth R esearch A uthority
НТА	H uman T issue A uthority
NICE	N ational I nstitute for Health and C are E xcellence
NHS	N ational H ealth S ervice
MHRA	M edicines and H ealthcare Products R egulatory A gency
MID	M icrobiology and Infectious D isease
NRES	N ational R esearch E thics S ervice
PI	P rincipal I nvestigator
PIS	Participant Information Sheet
R&D	R esearch & D evelopment
REC	R esearch E thics C ommittee
SAE	S erious A dverse E vents
SDL	S tudy D elegation L og

Project Proposal – V6.0 –07/09/2020

SOPs	S tandard O perating P rocedure(s)
SNOT-22	S ino- N asal O utcome T est
TMF	T rial M aster F ile
UHB	U niversity H ealth B oard
UKCRN	U nited K ingdom C linical R esearch N etwork

Bwrdd Iechyd Prifysgol Caerdydd a'r Fro Cardiff and Vale ALES Cardiff and Vale University Health Board

3. Trial Background and Rationale

Cystic fibrosis (CF) is an inherited lifelong, life threatening disease which can affect multiple organs in the body. The inherited defect affects a cells chloride ion channels leading to thick and sticky secretions. This is highly problematic in the lung where there is an accumulation of mucus, which in turn blocks the airway and leads to increased breathing difficulties. In addition to this, the mucus acts as a rich nutrient source that promotes colonisation by a wide range of bacterial species, such as; Staphylococcus aureus, Pseudomonas aeruginosa and Burkholderia cepacia complex species. As infection and lung damage progress over the years, P. aeruginosa becomes the dominant infective species, accounting for 33% of all UK CF lung infections, with 55% of patients prescribed long term inhaled antibiotics to help try and prevent/remove these infections (ECFSPR Annual Data Report 2013). Long term exposure to antibiotics leads to the emergence of Antimicrobial Resistance (AMR) amongst bacterial cells, which is now recognised globally as one of the major threats to human health. Globally, 700,000 people die each year as a result of AMR, requiring the UK government to develop a 5 year plan in order to combat AMR (O'Neill 2014). The direct effects of AMR are far reaching, resulting in; an inability to control infections (which we once could with the same antimicrobial agents), increased morbidity, increased mortality, and decreased patient wellbeing, all of which lead to increased healthcare costs (Roberts 2009; Romling 2014). The upper respiratory tract (upper airways and sinuses) of CF patients are frequently infected and therefore act as reservoirs of infection for the lower respiratory tract (Johansen 2012). Therefore, we have an urgent need for new and sustainable antimicrobial treatments for those suffering with CF as over 80% of patients will require treatment as a result of chronic infection and subsequent inflammation which ultimately leads to lethal respiratory failure (Lyczak 2002).

To understand the impact (emotionally and socially) of CF and the treatments on everyday life, a specialised questionnaire way developed (CFQ-R) to aid healthcare professions in how they tackle patient health and treatment. In addition to this, patients undertake a Sino-Nasal Outcome Test (SNOT-22) questionnaire which determines the social and emotional consequences of the patient's nasal disorder. If scoring highly in this, patients are required to follow a nasal rinse procedure daily as part of standard clinical care to help alleviate some of the symptoms described above.

Manuka honey has a strong track record as an antimicrobial agent, inhibiting a wide range of opportunistic pathogens, many of which cause problematic chronic infections, and can colonise the Project Proposal – V6.0 –07/09/2020

CYMRU CAerdydd a'r Fro Caerdydd a'r Fro Cardiff and Vale University Health Board

airway of CF patients (Cooper 2008; Jenkins 2015; Roberts 2012). It is thought that by combining manuka honey with the nasal rinse procedure, the patients emotional and social wellbeing (as determined by the two questionnaires) may improve and the amount/diversity of bacterial cells within the sino-nasal area might also be lowered and/or altered.

As part of routine care, patients with CF have an annual review meeting which involves attending the All Wales Adult Cystic Fibrosis (AWACF) Centre at the University Hospital Wales (UHW) Llandough. During this meeting nasal swabs, blood tests, sputum samples, chest X-rays and an assessment of sinus symptoms (via the SNOT-22 and CFQ-UK) is completed. They also attend other routine clinics during the year and can have stays as in patients. Over an 18-month period, some of these patients (which meet the set inclusion criteria) will be recruited to the study. Prior to the routine clinic meetings, patients are reminded (via) letter about their upcoming meeting. We intend to include information about this study and a patient information leaflet within this letter.

During any routine clinic meeting, patients scoring highly on the SNOT-22 questionnaire will be asked whether they wish to take part in the study. The healthcare professionals will ensure the patient has read the information leaflet, answering any questions they may have with regards to the study. Patients who wish to proceed will be asked to give informed consent and will become a participant of the study. Participants will be randomly assigned into two groups; Group one will follow the standard NHS nasal rinse protocol, and group two will follow a modified NHS nasal rinse protocol which requires the addition of manuka honey (supplied to the participants). Participants will then follow the nasal rinse procedure (with/without manuka honey) daily for 30 days.

As part of routine clinical care, patients return to the AWACF centre approximately one month after routine clinic meeting. During this meeting the same tests are completed and their results from the previous meeting are explained to them. A treatment plan is then agreed with the patient. Participants of the study will supply a nasal swab, sinus rinse sample, and sputum sample (all part of standard care) along with copies of their SNOT-22 and CFQ-UK questionnaires. Any effects manuka honey has on the questionnaire scores, the amount/diversity of bacteria within the sino-nasal area, and/or the structural composition of the sputum will be analysed and determined.

Conventional microbial culture analysis will be completed along with microbiota analysis using DNA extracted from bacteria within sputum, sinus rinse, and swab. This high resolution, cultivation independent method analyses all the bacteria present in the samples including those that are deemed "unculturable". Understanding the total microbiota and the effect of honey on these organisms will provide an all-encompassing picture of the therapeutic benefit the proposed sinus rinse protocol. Fourier transform infrared spectroscopy will be used to determine if the manuka honey rinse protocol causes any molecular structural changes to sputum mucus (secreted mucin glycoprotein) composition as mucin glycan composition maybe an indicator of disease state in cystic fibrosis (Schulz et al., 2007).

A clear picture that has emerged from the application of microbiome analysis to CF lung infections is that as patients age, accumulating multiple rounds of potent antibiotic therapy, the diversity of the bacteria in the lung reduces. Their infections become dominated with AMR infections such as Pseudomonas and Burkholderia. This low diversity state is commonly associated with severe lung disease and inflammatory damage (Li 2016).

The proposed sample size combines a power calculation and a consideration of logistical constraints. We expect to see 290 patients per year of which 50% should complete a SNOT-22 form. Of the 145 forms received around 72 (50%) should be above average. If we allow for a low recruitment rate (of 30-40%) we believe it is realistic to enrol at least 20-30 patients per year. Over the 18 months of the project we feel, therefore, a sample size of 30-40 can be realistically achieved. Savastano (2014) published summary details of SNOT-22 scores for CF patients (who should well approximate our sample group) reporting a mean (SD) scores of 30.5 (14.5). We draw our definition of a clinically significant change from Hopkins et al (2009), who propose 8.9 points. The study will be structured as a 2-sided equality trial, with before and after measurements for each participant. In order to obtain a power of 80% we would require a sample size of at least 21.

We appreciate that the numbers of participants that will be recruited for this study, within the time frame (between 20-40 in 18 months), is not a true representation of the national population of CF patients. However, the results of this feasibility/pilot study will identify any trends in the effects of a nasal rinse supplemented with manuka honey on the bacterial amount/diversity within the infected sinuses. Antimicrobial interventions that do not rely on antibiotics to remove resistant strains from sinus infections have the potential to help alleviate symptoms in the sinus and upper airways, which may impact on the bacteria seen in the lower airways (Aanaes, 2013). Therefore, if a change in Project Proposal – V6.0 - 07/09/2020

bacterial diversity or a reduction in symptoms is observed, this study could inform a more in-depth study as manuka honey has already been demonstrated to eradicate both antibiotic sensitive and AMR bacteria in vitro and from chronic in vivo wounds.

Helping to manage upper respiratory infections without antibiotics could help to reduce an important driver for AMR, reduce the potential of cross contamination by AMR bacteria and help to reduce excessive healthcare costs. The research team have a wealth of experience in this area so are well placed to ensure a robust, well executed study that has the potential to inform and strongly influence treatment planning choices in the future, and ultimately improve the health outcome for patients. The information gained from this study would likely have impact on both clinical practitioners and patients in the long term, as demonstrating the presence of AMR could lead to a change in treatment regimens and help with reducing excessive healthcare costs.

4. Objectives and Outcome Measures/Endpoints

4.1 Primary Objectives

Objective	Outcome Measure / Endpoint	
Does the addition of manuka honey to the sinus rinse impact on the SNOT-22 score of patients with cystic fibrosis?	SNOT-22 scores will be completed before and after the use of a sinus rinse with/without manuka honey.	

4.2 Secondary Objectives

Objective	Outcome Measure / Endpoint
Does the addition of manuka honey to a sinus rinse alter the quality of life of patients with cystic fibrosis?	Quality of life questionnaires (CFQ-R) will be completed before and after the use of a sinus rinse with/without manuka honey.
Does the addition of manuka honey to a sinus rinse impact on the bacterial type/amount found in the nasal/paranasal cavities of patients with cystic fibrosis?	Swabs, a sinus rinse wash sample and a sputum sample for each participant will be collected before and after the use of a sinus rinse with/without manuka honey. Bacteria amount and types will be analysed in each sample.
Does the addition of manuka honey to a sinus rinse protocol change the structure of sputum mucus in patients with cystic fibrosis?	Sputum samples from each participant will be analysed before and after the use of a sinus rinse with/without manuka honey by fourier transform infrared spectroscopy.

Bwrdd lechyd Prifysgol Caerdydd a'r Fro Cardiff and Vale University Health Board

5. Study Design

This is a single site study to be run at the AWACFC based in University Hospital Llandough (Cardiff and Vale Health Board) when patients attend any routine clinic meeting. The work on site will be carried out by the clinical research team as per the delegation of duties log.

The AWACFC cares for 300 adults with CF from across Wales. Under standard clinical practise (NICE and CF Trust) all patients with CF receive an annual review meeting and routine clinic meetings each year as part of their routine clinical care. The AWACFC routinely write to patients who are due to attend the centre for their meetings with information explaining the meeting process. We intend to include information about this study, a patient information sheet and a patient consent form. During their meeting, participants who report significant nasal symptoms (measured using the SNOT-22 questionnaire) will be asked whether they wish to take part in this study. The clinical research team will check that patient has read the patient information sheet and answer any questions they may have. If patients want more time to think about the study, a separate clinic appointment can be arranged to accommodate this need. Patients who have given informed consent will become a participant of the study and be randomized to one of two groups; those who will use the standard sinus rinse (group one) and those who will have manuka honey added to the sinus rinse (group two). The participants will use their supplied nasal rinse protocol (with/without manuka honey) daily for 30 days while also filling in a participant compliance diary.

The study will not involve additional clinic visits for patients, however a nasal swab and sinal rinse solution would be provided in addition to standard measurements.

Bwrdd lechyd Prifysgol Caerdydd a'r Fro Cardiff and Vale University Health Board

6. Study Management

The trials management group (consisting of [name], [name], [name], [name], [name], and [name]) will meet up every 3 months and will be in contact via email and phone during the interim if any part of the study needs discussing. The full list of duties is outlined in the delegation of duties log. Standardized SOPS for each clinical procedure will be followed for each activity.

7. Study Flow Chart

Bwrdd lechyd Prifysgol Caerdydd a'r Fro Cardiff and Vale University Health Board

8. Participant Identification

Between 20-40 patients will be recruited for this study over an 18-month period. Patients will be recruited opportunistically during their routine clinic meetings. Normally the AWACFC runs a clinic for CF patients everyday Monday to Friday. We would estimate recruiting an average of two patients per month, taking into account the inclusion/exclusion criteria (see below), and the potential for participants to drop out of the study. We would expect to recruit all patients within the 18-month period.

8.1 Inclusion Criteria

The following criteria will be used to determine the eligibility of a patient to participate in the study.

- The patient is willing and able to give informed consent.
- The patient must be \geq 18 years.
- The patient must have an established diagnosis of CF (one or more of the following)
 - Sweat chloride >60mEq/L
 - Presence of two CF causing mutations.
- The patient must have chronic symptoms of rhinosinusitis according to the criteria of the European Position Paper on Rhinosinusitis (appendix A).
- The patient scores greater \geq 7 on their SNOT-22 questionnaire.

8.2 Exclusion Criteria

The following criteria will be used to determine the ineligibility of a patient to participate in the study.

- The patient has ever tested positive for the bacteria Mycobacterium tuberculosis.
- The patient is currently using a nasal rinse protocol.
- The patient has undergone sinus surgery within 6 months.
- The patient suffers from nasal bleeding.
- The patient is currently undergoing systemic antibiotic therapy for infective exacerbation.
- The patient is using overnight oxygen via nasal cannula.
- The patient is participating in another clinical trial or has done so within the last 30 days.
- The patient has a known allergy to bee products.
- The patient has an objection to the use of bee products

Bwrdd Iechyd Prifysgol Caerdydd a'r Fro Cardiff and Vale University Health Board

9. Study Procedures

(See attached study procedures document)

9.1 Recruitment

A member of the clinical research team (as per the delegation of duties log) will identify potential participants when arranging their routine clinic meeting at the AWACFC. As part of the letter sent out informing the patient of their routine clinic meeting, the clinical research team will include a letter, patient information sheet, and patient consent form. This will allow the patient to read through the information prior to attending their routine clinic appointment. During this week period, they are able to call the clinical research team to ask any questions. At the meeting appointment, the patient will have another opportunity to ask questions about the study. These patients will be recruited opportunistically at their meeting if they meet the inclusion criteria without any excluding criteria.

All potential participants will be recruited from the AWACFC during routine clinical meeting. All data gathered during this process will only be seen by the clinical research team whom will also be delivering their standard care, so there should be no issues with confidentiality. This information will be passed onto the academic research team (as per the delegation of duties log) in an anonymised state so as to project the study participant.

Participants will provide answers to a SNOT-22 questionnaire as part of standard practice and if their score meets the inclusion criteria, the clinical research team will discuss the trial in detail with the patient. If the patient is happy to proceed, informed consent will be taken, and the patient will become a participant of the study immediately with all their data being randomised against a participant ID number. As per the patient consent form their GP will be subsequently notified of their involvement in the study. Participants will then be randomly separated into two groups:

- Group 1 Those who will use the standard sinus rinse.
- Group 2 Those who will use the standard sinus rinse with the addition of manuka honey.

During their routine clinic meeting (Visit 1), all participants of the study will provide the following data/samples:

• SNOT-22 questionnaire.

Project Proposal – V6.0 –07/09/2020

- Cystic Fibrosis Quality of life (CFQ-R) questionnaire.
- Clinical Record Form (CRF) data.
- Nasal swab.
- Sputum sample.
- Nasal rinse wash solution.

Participants will then be given a nasal rinse kit (with/without manuka honey depending on the group they have been assigned), a set of instructions on how to use the kit, and a compliance diary. Participants will use their respective kits as per the instructions daily and fill in the compliance diary, ensuring to make note of any observations in the compliance diary. Participants will then return to the AWACFC 31 days (+7/- 20 days) later for their standard follow up appointment (Visit 2). During this visit a second set of data/samples will be collected as per below:

- SNOT-22 questionnaire.
- Cystic Fibrosis Quality of life (CFQ-R) questionnaire.
- Clinical Record Form (CRF) data.
- Nasal swab.
- Sputum sample.
- Nasal rinse wash solution.

Following the collection of samples by the clinical research team during visit 1 and 2, they will be collected by the academic research team whom will process the nasal swab, sputum sample, and nasal rinse wash solution the same day, extracting bacteria and bacterial DNA from the samples. The structural composition of the sputum mucus will also be determined from the sputum sample. Other analysis of the samples we be completed at a later date where the amount/types of bacteria present will be determined.

9.2 Screening and Eligibility Assessment

Potential participants would be sent written information at least one week prior to their routine clinic meeting. At the routine clinic appointment an assessment of sinus symptoms is routinely performed by a respiratory physiotherapist. If patients describe sinus symptoms a SNOT -22 questionnaire is administered. The physiotherapist will inform the clinical research team who will then assess whether the patient meets the inclusion criteria for the trial and will take informed consent if the patient is keen to participate. In the study.

Bwrdd lechyd Prifysgol Caerdydd a'r Fro Cardiff and Vale S University Health Board

9.4 Randomisation, Blinding, and Unblinding

A blocked randomisation list will be generated prior to start of study using the electronic random number generator tool (see below). The participants of the study will not be blinded to the treatment they are receiving because the addition of manuka honey to the sinus rinse is obvious and there is no way to negate this. The academic research team will be blinded to which groups the participants (only identifiable by their participant ID number) are assigned. This information (the group allocations and treatment regimens) will only be made available to the academic research team once analysis of the data begins.

- GraphPad QuickCalcs
 - o https://www.graphpad.com/quickcalcs/randomize1/

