12.1 Description of Statistical Methods

Qualitative analysis will include the difference between the SNOT-22 and quality of life questionnaire (CFQ-R) scores being assessed before and after treatment within and between both patient groups (with/without manuka honey). To determine if manuka honey caused a change in the amount/type(s) of bacteria present compared to the control group, a contingency table with odds ratio will be prepared taking into account co variants. Infrared spectra will be baseline corrected and vector normalised. Absorbance from specific infrared wavenumbers representative of mucin glycan molecular structures will be compared against in-house sputum spectral libraries to determine increase or decrease in glycosylation patterns as well as structural changes post-treatment. Comparisons in absorbance at key wavenumbers between groups will be analysed using ANOVA.

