12.3 Analysis of Outcome Measures/Endpoints

All participant data will be analysed by the academic research team after the end point of the study. The data will be sorted into the two treatment groups before analysis is carried out. The

primary outcome measures will be to determine whether the SNOT-22 score of the manuka honey treatment group has improved compared to the standard treatment. The secondary outcomes will be to see if; the lifestyle questionnaire scores have improved, the amount/type(s) of bacteria has changed, and whether the structure/composition of sputum mucus has changed in the same two groups. If any participants withdrew before the second visit/second set of samples were taken then that data will be excluded from analysis.

Bwrdd lechyd Prifysgol Caerdydd a'r Fro Cardiff and Vale University Health Board

13. Data Management

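### Allocations reach the only blinded team when data analysis begins, before the supplied text fixes the score contrast, bacterial categories and key wavenumbers; lock these first, then analyse under masked arm labels

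*Combined protocol and SAP*

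**What the plan says.** Section 9.4 sets the blinding. On participants: "The participants of the study will not be blinded to the treatment they are receiving". On the laboratory and analysis side: "The academic research team will be blinded to which groups the participants (only identifiable by their participant ID number) are assigned". Allocations and regimens "will only be made available to the academic research team once analysis of the data begins".

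Section 12.3 gives the order of work. On who analyses, and when: "All participant data will be analysed by the academic research team after the end point of the study". On grouping: "The data will be sorted into the two treatment groups before analysis is carried out". The primary aim is stated in words, as determining "whether the SNOT-22 score of the manuka honey treatment group has improved compared to the standard treatment".

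Section 12.1 describes the methods:
- **Scores.** SNOT-22 and CFQ-R are compared before and after treatment, both within and between the groups.
- **Bacteria.** A contingency table with an odds ratio, allowing for covariates.
- **Spectra.** Baseline correction and vector normalisation, comparison with in-house libraries "to determine increase or decrease in glycosylation patterns as well as structural changes post-treatment", and ANOVA at key wavenumbers.

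Section 9.1 has the academic team process the specimens and extract bacteria and DNA on the day of collection. It leaves the determination of bacterial amounts and types to a later date.

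**The concern.** Participants know their treatment, and the clinic team hands out the arm-specific kits. The academic team's blinding is therefore the only blinding described. It protects most where a result depends on the analyst's judgement: which wavenumbers count as key, how the baseline is corrected, how bacteria are grouped, which specimen decides, and which covariates enter. If those decisions are still open when the arms are named, they can drift, without intent, toward the grouping or wavenumber that shows a honey effect.

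The consequence would be secondary results that are hard to defend. Pilot status does not remove this, because section 3 says that an observed change in bacterial diversity or symptoms could inform a more in-depth study.

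**Working it through.** **1. Order of events**

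| Step | Section | Allocation known to the academic team? |
|---|---|---|
| Same-day processing, extraction of bacteria and DNA | 9.1 | No |
| Processing finished and samples destroyed within 7 days | 9.7 | No |
| Later determination of bacterial amounts and types | 9.1 | Not clear |
| Data analysis begins; allocations and regimens released | 9.4 | Yes, from here |
| Data sorted by arm, then analysed | 12.3 | Yes |

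Section 9.1 places the determination of sputum structure alongside specimen processing, whereas section 12.1 lists spectral correction under statistical methods. Whether spectral correction is done before or after release is therefore also unclear.

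**2. What is fixed before release, and what is not**

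| Outcome | Named | Not fixed in the supplied text |
|---|---|---|
| SNOT-22, CFQ-R | Between-arm aim, in words (12.3); within- and between-group comparison (12.1) | Test, change or follow-up score, baseline adjustment, CFQ-R domain, weight of the within-group comparison |
| Bacteria | Contingency table, odds ratio | Categories, covariates, deciding specimen |
| Mucus spectra | Baseline correction, vector normalisation, in-house library, ANOVA | Wavenumber list, correction settings, handling of several wavenumbers |

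The supplied text describes no data lock, no sign-off of these choices and no masked arm coding before release.

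**3. The plan's own figure**

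The concern is about procedure, so it changes no stated number. For completeness, the minimum of 21 in section 12.2 reproduces with SD 14.5, difference 8.9, 80% power and an assumed two-sided alpha of 0.05, using the paired (one-sample) formula:

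n = (SD × (1.960 + 0.842) / difference)² = (14.5 × 2.802 / 8.9)² = 20.83, rounded up to 21.

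**4. What open choices cost, and whether masking would help**

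Assumptions: no honey effect, 15 per arm (half of the target of 30), two-sided alpha 0.05, and a baseline to follow-up correlation ρ of 0.3, 0.5 or 0.7, which the documents do not give. On a standardised scale, follow-up = ρ × baseline + √(1 − ρ²) × independent noise. With 20,000 simulated trials per ρ:

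| ρ | Any of follow-up, change or ANCOVA below 0.05 | Same, plus the within-honey test |
|---|---|---|
| 0.3 | 9.1% | 12.0% |
| 0.5 | 9.4% | 12.4% |
| 0.7 | 10.0% | 13.0% |

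The smallest two-sided p-value of the three between-arm tests does not change when the arm labels are swapped. An analyst who sees only A and B and picks the best of those three reaches the same 9–10%. About half of those results favour honey: roughly 4.5–5%, against a nominal 2.5%. The figure therefore measures the cost of an unspecified SNOT-22 test. The lock corrects that cost; the masked labels do not.

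The within-group comparison needs the lock too. If both arms improve equally by 8.9 points, the within-honey test alone is significant in 47%, 60% and 81% of trials at ρ = 0.3, 0.5 and 0.7, although honey adds nothing.

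No comparable calculation is possible for bacteria or spectra, because the text gives no number of candidate categories or wavenumbers.

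**The case against.** The strongest reply has four parts.

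- **Much judgement is already blind.** Specimen handling and extraction come before release, under ID numbers only. Since section 9.4 ties release to analysis of the data, bacterial identification and mucus measurement may also be finished blind. The first statement stands. The second is a possible reading, but the text does not settle it, and choosing categories and wavenumbers for comparison remains part of the data analysis either way.
- **The methods are partly set, and more may be set elsewhere.** Three spectral steps are named. Section 9 points to an attached procedures document, and sections 6 and 9.7 to SOPs, none of them supplied. This stands as a limit: if those documents fix the lists, the protocol need only cite them.
- **The consequence is limited.** The outcomes most affected are secondary in a pilot, and the primary score is self-reported by participants who know their arm. That stands, and it lowers the weight of the point without removing it.
- **Masking is an add-on.** A and B labels hide direction, not significance. That is right, which is why the lock comes first.

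A reader might also infer that the same individuals process samples and choose the analyses. The documents name the same team; individual duties sit in a delegation log that is not supplied.

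**Conclusion.** The point holds as a matter of sequence. The only described blinding ends when data analysis begins, and the supplied text does not fix the remaining analytic choices before then. It matters most for the bacterial and mucus outcomes, and its size there cannot be calculated from the documents. The conclusion assumes that the unsupplied procedures document and SOPs do not already fix these choices.

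Three stronger readings are tempting and are not supported:
- That unblinding doubles the false-positive rate to 9–10%. That figure comes from leaving the SNOT-22 test open, is the same under masked labels, and says nothing about the other outcomes. Nor can the freedom in wavenumbers or taxa be called larger.
- That blinding ends before any judgement is exercised. Sample processing and extraction are done blind.
- That later release would protect the questionnaire scores from reporting bias. Participants are unblinded throughout.

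This is a cheap improvement, not a flaw that undermines the design.

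**What to change.** Amend sections 9.4 and 12.3 to state, in this order:

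1. Before any allocation is released, the following are locked: the data, the primary SNOT-22 contrast, the bacterial categories and covariates, the wavenumber list and pre-processing settings, and the analysis code. Anything already fixed in the study procedures document or an SOP is cited instead.
2. The holder of the link code (the PI, under section 13.2) then supplies the academic team with labels A and B only.
3. The identity of the honey arm is released after the primary and secondary tables have been produced.

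No extra patients, visits or samples are needed. The cost is a short analysis plan written before release, including category and wavenumber lists that have to be chosen at some stage anyway. Under section 9.9 the sponsor must classify the change, and an amendment may need approval.
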